Official title: Maximizing Use of Continuous Positive Airway Pressure in Stroke Rehabilitation Patients With Obstructive Sleep Apnea

NCT number: 02809430

Document date: March 10, 2019

Design: Single-arm, open-label study

Objectives: To assess the effectiveness of a multifaceted and intensive adherence program on 3month CPAP adherence and measures of stroke outcome (NIH stroke scale and Functional Independence Measure) among stroke patients undergoing inpatient rehabilitation (IPR)

Methods:

Eligible stroke patients (Table I) were enrolled and trialed auto-adjusting CPAP (4–20 cm H2 O; Dream Station, Philips Respironics) over a 3-night run-in period during IPR. Devices were interrogated for nightly usage, average pressure, and a residual apnea-hypopnea index (the respiratory events per hour of sleep). At the end of the run-in period, evidence of OSA was determined based on airflow resistance detected by the machine (see diagnosis of OSA below). Patients with evidence of OSA were eligible for CPAP treatment during IPR and after discharge from IPR. Nurses, respiratory therapists, sleep technologists, and clinical psychologists initiated the SCOUTS intensive CPAP adherence protocol during IPR emphasizing early CPAP tolerance, individual motivation (Table II) and support throughout the treatment period. The primary end point was CPAP adherence over 90 days from CPAP initiation, defined as \geq 4 hours of use on \geq 70% of days. Secondary efficacy end points were changes in the motor and cognitive components of the Functional Independence Measure (FIM) between admission and 3 to 4 months after discharge from IPR and in the National Institutes of Health Stroke Scale (NIHSS) between enrollment and 90 days.

Diagnosis of obstructive sleep apnea (OSA)

To avoid delays inherent to administering formal sleep studies and interpreting results during inpatient stroke rehabilitation, we utilized device detected flow resistance. Study participants were started on an auto-adjusting CPAP machine (DreamStation, Philips Respironics) both to rapidly diagnose OSA and to provide earlier treatment.^{1, 2} After a 3-night run-in period during inpatient rehabilitation, auto-adjusting CPAP devices were interrogated for the mean pressure over the run-in period and the nightly residual apnea-hypopnea index, based on flow measurements (AHI_{Flow}). The diagnosis of OSA was determined based on data from the CPAP device downloads using one of two criteria: 1) average airflow limitation over the entire run-in period, defined as mean CPAP pressure $\geq 5 \text{ cm H}_2\text{O}$ over a minimum of 3 hours of use, OR 2) on-treatment AHI_{Flow} ≥ 5 events/hour on any of the 3 nights. Participants were excluded if the download showed evidence of central sleep apnea with a clear airway index ≥ 10 or of complex sleep apnea with an AHI_{Flow} ≥ 25 .

SCOUTS Intensive CPAP Adherence Program (iCAP)

To improve CPAP use, a SCOUTS iCAP was initiated during IPR and targeted 3 aspects of adherence: CPAP tolerance, motivation and support. To improve CPAP tolerance, rehabilitation nurses, respiratory therapists and sleep technologists led an iterative process of device adjustments, mask interface changes, OSA education and encouragement. To enhance motivation for CPAP use, patients watched a patient testimonial video on CPAP and stroke

recovery and met with a clinical psychologist for motivational interviewing (MI) during IPR to discuss patients' readiness to change, confidence in using CPAP and coping techniques to adjust to CPAP use (see Table II). The 30-minute face-to-face MI sessions occurred within one week of starting auto-adjusting CPAP. The MI session were focused on building motivation to use CPAP and alter the subject's decisional balance about using CPAP as it relates to patient-specific goals. To improve support, the adherence program included nightly visits by respiratory therapists during IPR to improve self-efficacy with CPAP and tailored written feedback prior to discharge from the IPR unit detailing CPAP download data, adjustments made during IPR and goals and barriers for CPAP use. Phone calls were also made weekly for one month after discharge from the IPR unit to encourage CPAP use and troubleshoot any device or mask problems.

Efficacy Measures

The National Institutes of Health Stroke scale (NIHSS; range, 0 to 42; higher scores indicate greater neurologic impairment) scores were obtained in-person on enrollment and at 90 ± 7 days from enrollment. The Functional Independence measure (FIM) scores were obtained as part of routine clinical care. The FIM included a motor and cognitive component (motor range, 13-91; cognitive range, 5 to 35; lower scores indicate greater functional disability). The admission FIM scores were obtained in-person by rehabilitation nurses and therapists upon admission to the IPR unit and follow-up FIM scores were obtained as part of routine clinical care through phone interview by IT Health Track, Inc., between 3 and 4 months from IPR unit discharge (mean 106 days); telephone response rates are approximately 60%.

Statistical Analyses

We compared baseline demographics, stroke severity and rehabilitation characteristics by adherence, using t-tests and Chi-squared tests as appropriate. To evaluate for predictors of adherence (Table III), we performed logistic regression, adjusting for baseline demographic covariates determined *a priori* including age (≥ 65 years), race/ethnicity (White versus non-White or Hispanic), sex, obesity (body mass index ≥ 30 kg/m²), baseline NIHSS score ≥ 5 and inpatient rehabilitation length of stay (weeks). As those with aphasia were noted to be adherent to CPAP, we added this stroke characteristic into separate models post-hoc.

We examined for differences in baseline, 3-month and changes between baseline and 3- months in NIHSS, motor FIM and cognitive FIM by CPAP adherence using the t-test with unequal variances (Table IV). We also evaluated for association of CPAP adherence with 3-month NIHSS and cognitive FIM change using linear regression in models adjusting for age ≥ 65 years, sex, race/ethnicity, body mass index ≥ 30 , and baseline NIHSS score at study enrollment (Table IV). Finally, we evaluated the proportion of adherent and non-adherent participants who had improvement in the cognitive FIM and NIHSS, which was greater than the mean improvement among the entire sample: ≥ 7 for cognitive FIM improvement and ≥ 4 for NIHSS improvement (Table V).

Table I. Main Selection Criteria

Inclusion Criteria

Informed consent

Acute ischemic stroke or intraparenchymal hemorrhage

Age \geq 18 years

Admission to inpatient stroke rehabilitation unit at Harborview Medical Center and the University of Washington Medical Center

Exclusion Criteria

Stroke related to bleeding disorder, substance abuse, tumor, vascular malformation, trauma or other secondary cause

Active CPAP use at time of enrollment

Advanced congestive heart failure (New York Heart Association class 3 or 4)

Requiring supplemental oxygen or nasogastric feeding tube

Participation in another research outcome study

Table II. Motivational Interviewing Data Form

Subject's understanding of stroke and sleep apnea:

- Subject's readiness to change:
- □Pre-contemplation
- □Contemplation
- □Preparation
- \Box Action
- □Maintenance

Any small achievable subgoals:

 \Box YES \Box NO

Subject's reason for using CPAP:

□Stroke prevention

□Stroke recovery

□Sleep improvement

 $\Box Other$

Subject's reason for not using CPAP:

□Claustrophobia

□Anxiety

□Sleep disturbance

 \Box Mask fit or leak problems

□Device problems

 $\Box Other$

On a scale of 1-10, how important do you think it is for you to treat sleep apnea and use the

CPAP device?

On a scale of 1-10, how confident are you in your ability to use the CPAP device from now until the next time we meet?

Table III. Baseline factors associated with 3-month CPAP adherence, odds ratio (95% confidence interval)*

*All models included age, sex, obesity and weeks on inpatient rehabilitation. Model 1 additionally included race and baseline NIHSS \geq 5; model 2 for race and aphasia; model 3 for race, aphasia and baseline NIHSS \geq 5.

	Model 1	Model 2	Model 3
White race	10.9 (1.7, 701)	3.7 (0.7, 19.8)	8.2 (1.1, 62.3)
Aphasia		12.9 (1.3, 129)	8.0 (0.7, 87.7)
NIHSS≥5	14.9 (1.9, 115.7)		10.6 (1.2, 92.6)

	Adherent, mean (SD)		Non-adherent, mean (SD)			P-value*		
	Baseline	3-months	Change	Baseline	3-months	Change	Unadjusted	Adjusted
Motor FIM†	48.5 (11.2)	79.7 (12.1)	31.2 (15.7)	47.3 (17.6)	77.5 (10.8)	30.2 (13.2)	0.83	0.65
Cognitive FIM†	24.1 (6.9)	32.4 (3.7)	8.2 (6.5)	28.5 (3.9)	33.1 (2.4)	4.6 (3.0)	0.03	0.02
NIHSS ‡	6.5 (4.3)	2.7 (3.1)	-3.8 (2.6)	4.1 (2.2)	2.6 (2.6)	-1.6 (2.2)	0.003	0.03

Table IV. Improvement in cognitive FIM and NIHSS associated with CPAP adherence

CPAP indicates continuous positive airway pressure; SD, standard deviation; NIHSS, National Institutes of Health Stroke Scale; Cognitive FIM, cognitive component of Functional Independence measure

* Difference between mean changes in outcome between adherent and non-adherent patients: unadjusted using t-test with unequal variances and adjusted for age, sex, body mass index, race and baseline NIHSS using linear regression

† n=22 adherent group and n=12 non-adherent

‡ n=30 adherent group and n=19 non-adherent

Table V. Improvement in cognitive FIM and NIHSS associated with CPAP adherence

Patient characteristics	Adherent	Non-adherent	P -value
Cognitive FIM improvement ≥ 7, n (%)*	10 (45)	3 (25)	0.24
NIHSS improvement \geq 4, n (%) [†]	16 (53)	3 (16)	0.01

* n=22 adherent group and n=12 non-adherent

† n=30 adherent group and n=19 non-adherent

REFERENCES

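### Table III fits 6 or 7 terms, apparently by unpenalised logistic regression, to about 19 non-adherent participants (inferred), and labels as baseline a length of stay that ends after the adherence window opens (minor, secondary table only)

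*Combined protocol and SAP*

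**What the plan says.** In the combined protocol and SAP, Statistical Analyses describes the predictor models as "adjusting for baseline demographic covariates determined" a priori, and the list closes with "baseline NIHSS score ≥ 5 and inpatient rehabilitation length of stay (weeks". The Table III footnote confirms the adjustment: "All models included age, sex, obesity and weeks on inpatient rehabilitation". Model 1 adds race and NIHSS ≥ 5, Model 2 adds race and aphasia, and Model 3 adds all three. Aphasia was not in the a priori list: "we added this stroke characteristic into separate models post-hoc".

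On timing, Methods defines the primary end point as "CPAP adherence over 90 days from CPAP initiation". The section on diagnosis of OSA places the start of CPAP inside the rehabilitation stay ("After a 3-night run-in period during inpatient rehabilitation", the device is read out).

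Table III prints odds ratios with 95% intervals, for example "14.9 (1.9, 115.7" for NIHSS ≥ 5 in Model 1. It gives no N, and no penalised or exact method is mentioned. The footnotes to Tables IV and V give 30 adherent and 19 non-adherent participants for the NIHSS comparison. The Table IV regressions adjust for age, sex, race/ethnicity, body mass index "and baseline NIHSS score at study enrollment (Table IV", and do not include length of stay.

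**The concern.** Table III is the only multivariable analysis of what predicts adherence, and it prints odds ratios of 8 to 15 for NIHSS and aphasia. Figures of that size tend to be quoted.

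Two features affect how they should be read. Maximum-likelihood logistic regression with few participants per term in the smaller outcome group exaggerates real associations on average, most of all when they are strong. A wide interval shows imprecision, but it does not move an exaggerated point estimate back.

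Separately, a covariate called baseline is normally fixed before follow-up starts. Length of stay is fixed at discharge, after the adherence window has opened. It may lie between stroke severity and adherence, or share causes with adherence. A reader guided by the baseline label could take the printed odds ratios as total baseline associations, when they are associations given length of stay.

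**Working it through.** **Fitting method.** The plan states no sample-size or precision figure for Table III, so the first check is on the printed intervals. A Wald interval is symmetric on the log scale, so √(lower × upper) should return the odds ratio.
- NIHSS: √(1.9 × 115.7) = 14.8 (printed 14.9); √(1.2 × 92.6) = 10.5 (10.6).
- Aphasia: √(1.3 × 129) = 13.0 (12.9); √(0.7 × 87.7) = 7.8 (8.0).
- White race, Models 2 and 3: √(0.7 × 19.8) = 3.7 (3.7); √(1.1 × 62.3) = 8.3 (8.2).
- White race, Model 1: √(1.7 × 701) = 34.5 (10.9). This cell does not match and is not used.

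Six of seven cells fit Wald intervals from ordinary maximum likelihood. The implied standard errors of the NIHSS log odds ratio are ln(115.7/1.9)/3.92 = 1.05 and ln(92.6/1.2)/3.92 = 1.11.

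**Participants per term.** Terms: 4 common + 2 = 6 (Models 1 and 2); 4 + 3 = 7 (Model 3). Taking 19 as the smaller group, 19/6 = 3.2 and 19/7 = 2.7. Over an assumed 15 to 25 the ranges are 2.5 to 4.2 (6 terms) and 2.1 to 3.6 (7 terms). At 30 they are 5.0 and 4.3.

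**Expected inflation.** Simulation with n = 49, 2,500 replicates per setting and 30/49 adherent. Assumed prevalences: age ≥ 65 0.35, sex 0.35, obesity 0.50, White 0.65 (OR 3), NIHSS ≥ 5 0.50, aphasia 0.25 (OR 3, 7-term model only). Length of stay had no effect. Entries are the exponentiated mean log odds ratio for NIHSS ≥ 5, 6 / 7 terms:

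| True OR | Maximum likelihood | Firth |
|---|---|---|
| 1 | 1.0 / 1.0 | not needed |
| 2 | 2.3 / 2.5 | 2.0 / 2.1 |
| 4 | 5.5 / 5.6 | 4.1 / 4.0 |
| 10 | 16.7 / 18.9 | 10.3 / 10.4 |

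Separated or non-converged maximum-likelihood fits (0.2–4.7% with 6 terms, 5.4–9.2% with 7) were excluded from the maximum-likelihood results. Wald coverage was 0.94 to 0.98; Firth profile-likelihood coverage was 0.95 to 0.96. Two further runs at n = 49 gave 5.5 / 5.9 and 5.6 / 5.9 at OR 4, and 18.7 / 19.6 and 17.9 / 19.5 at OR 10; Firth gave 4.1 and 10.6 to 11.1. A simulation with exactly 30 and 19 and other prevalences (0.3 to 0.65) gave 7.2 / 7.9 at a true OR of 5, against 5.1 / 5.2 by Firth. With four times the sample, maximum likelihood fell to 5.4 (6 terms).

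Relative to the printed standard errors, the bias at OR 4 is 0.32/1.05 = 0.30 and 0.34/1.11 = 0.31. At OR 10 it is 0.51/1.05 = 0.49 and 0.64/1.11 = 0.58.

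**Timing of length of stay.** CPAP starts during the stay, the adherence window opens at CPAP initiation, and the stay ends at discharge. Its total is therefore known only after the window opens, and its later nights fall inside the window. All three models contain it, so every printed odds ratio (race, NIHSS, aphasia) is conditional on it.

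The documents give no mean, spread or coefficient for length of stay, so no effect can be calculated. Purely as illustration, suppose NIHSS ≥ 5 adds one week and each week changes the log-odds of adherence by 0.4. A conditional OR of 4.0 then becomes 5.7 without length of stay if a longer stay raises adherence, and 2.6 if it lowers it. These inputs are invented; they show only that the sign is open.

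**A comparison without length of stay.** Table IV prints baseline NIHSS of 6.5 (SD 4.3, n = 30) in adherent and 4.1 (SD 2.2, n = 19) in non-adherent participants. SE = √(4.3²/30 + 2.2²/19) = 0.93, t = 2.4/0.93 = 2.57, and the Welch p is about 0.013. The unadjusted difference points the same way as Table III.

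**The case against.** The strongest case for leaving Table III alone has four parts.

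- **The adjustment is disclosed and was chosen a priori.** The footnote says beside the results that weeks on rehabilitation are in every model. Therapists visited every night of the stay, so adjusting for supervised exposure is a reasonable choice. This stands. It is why the adjusted fits should remain the main display, and why the complaint is about the label and the missing comparison. Choosing a covariate in advance does not make it a baseline measurement.
- **The intervals already show how little is known.** This largely stands: coverage is near nominal, and the expected bias is a fraction of one standard error. It does not repair the point estimates.
- **The count of 19 is borrowed.** It comes from the 90-day NIHSS set, whereas Table III needs only device data and baseline measurements, so its set may be larger. True, and the lower end of the assumed range has no basis in the documents. Even at 30, however, there would be only 4.3 to 5.0 per term.
- **Other comparisons exist.** The plan also compares baseline and rehabilitation characteristics by adherence with t-tests and Chi-squared tests. A reader might infer that Table III is the only analysis of adherence factors; it is only the only multivariable one. The NIHSS association also appears without length-of-stay adjustment, although an unadjusted difference in means does not supply an adjusted odds ratio.

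**Conclusion.** The point holds as a minor one, limited to a secondary table. With about 2.7 to 3.2 non-adherent participants per term, maximum-likelihood odds ratios for real associations are expected to be inflated on average: about 5.5 to 5.9 for a true 4, and about 17 to 20 for a true 10. Firth gives about 4.1 and 10 to 11. This rests on the inferred count of 19, the assumed prevalences, and the reading of the intervals as ordinary Wald intervals. The baseline label on length of stay is wrong on the plan's own timing.

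A reader might infer two stronger things that the documents do not support. One is that a particular printed figure, such as the NIHSS odds ratio of 14.9, is inflated by a known amount, or that the associations are spurious. Inflation is an average tendency, is absent at an odds ratio of 1, and cannot be shown for a single estimate. The other is that adjusting for length of stay biased Table III in a known direction, so that fits without it should replace the adjusted ones. Neither the direction nor the size can be derived, and a replacement chosen after the results were seen would itself be open to criticism. The primary adherence proportion does not use these models, and Table IV omits length of stay.

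**What to change.** - Re-fit the three models with Firth penalised logistic regression and profile-likelihood intervals. Keep the a priori covariate set, including length of stay, as the main display, and keep the models with aphasia marked post hoc.
- Add the same fits without length of stay, labelled as a post hoc sensitivity analysis. A difference between the two sets is not by itself a measure of bias, because odds ratios can change when a covariate is dropped even without confounding.
- Stop calling length of stay a baseline covariate, and state that the odds ratios are conditional on it.
- Report N and the adherent and non-adherent counts for each model.

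The cost is three to six re-fits on existing data and a few words of text. The Firth odds ratios are expected to be smaller than those printed; the fits without length of stay may move either way.

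### Age, BMI and (in Table III) NIHSS are modelled as yes/no cut-offs although a linear term costs the same one parameter; a sensitivity re-run with numeric terms is warranted, as a minor point

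*Combined protocol and SAP*

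**What the plan says.** - **Table III (logistic models for adherence).** The Statistical Analyses section describes these as "adjusting for baseline demographic covariates determined *a priori* including age (≥ 65 years"), with "obesity (body mass index ≥ 30 kg/m²") and "baseline NIHSS score ≥ 5 and inpatient rehabilitation length of stay (weeks"). Length of stay is the only covariate kept numeric. The Table III footnote confirms the severity cut: "Model 1 additionally included race and baseline NIHSS" at or above 5. Model 2 has race and aphasia without NIHSS, and model 3 has all three.
- **Table IV (linear models for outcome).** The same section describes models "adjusting for age ≥ 65 years, sex, race/ethnicity, body mass index ≥ 30", "and baseline NIHSS score at study enrollment (Table IV"). Age and BMI are cut; NIHSS is a score with no cut-off. The Table IV footnote lists the same covariates without restating the coding.
- **Availability of numeric values.** Efficacy Measures defines the scale as "NIHSS; range, 0 to 42; higher scores indicate greater neurologic impairment", and Table IV prints baseline means and SDs. Cuts at 65 years and 30 kg/m² imply that age and BMI were held as numbers.
- The document gives no reason for the cut-offs and no sensitivity analysis with numeric terms.

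**The concern.** A cut-off treats everyone on one side of it as alike. Where the true relation is graded, that has two consequences. First, the variable predicts less well, which matters for NIHSS in Table III, where it is a predictor of interest. Second, it adjusts less well when it serves as a confounder. That matters for severity when reading the race and aphasia odds ratios, and for age and BMI in Table IV. Adherence is not randomised in this single-arm study, so the Table IV contrast depends on its adjustment. The adjusted P-values there are 0.02 (cognitive FIM) and 0.03 (NIHSS), close enough to 0.05 for the quality of adjustment to matter. A small sample does not justify the cuts, because they save no degrees of freedom.

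**Working it through.** **Inputs.** From Table IV: baseline NIHSS 6.5 (SD 4.3), n=30 adherent, and 4.1 (SD 2.2), n=19 non-adherent; NIHSS change -3.8 (2.6) and -1.6 (2.2). From Table III: the printed odds ratios and 95% limits. Assumed: two-sided alpha 0.05; n=49 for Table III, which states no n; the shape of the NIHSS distribution; roughly normal age and BMI.

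**1. Reproducing a printed figure.** Welch test on NIHSS change: SE = √(2.6²/30 + 2.2²/19) = 0.693; t = -2.2/0.693 = -3.18; P = 0.0028 (printed 0.003). The adjusted P-values need patient data and cannot be checked.

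**2. Baseline severity by adherence.** SE = √(4.3²/30 + 2.2²/19) = 0.933; t = 2.4/0.933 = 2.57; P = 0.013. The pooled within-group SD is √[(29×4.3² + 18×2.2²)/47] = 3.64, so the shift is 2.4/3.64 = 0.66 SD.

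**3. Power for NIHSS as a predictor, unadjusted.**
- Normal approximation as a score: 2.4/[3.64×√(1/19+1/30)] = 2.25; Φ(2.25 - 1.96) = 61%.
- Same with a median cut (efficiency 2/π = 0.637): 2.25×√0.637 = 1.79; Φ(1.79 - 1.96) = 43%.
- Three separate simulations matched to the Table IV means and SDs gave 71% vs 42%, 70% vs 39% and 69% vs 35% (score vs cut-off).

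Power by assumed shape of the relation (slope is per NIHSS point; the step at 5 is scaled to match):

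| Slope | Graded: score / cut-off | Step at 5: score / cut-off |
|---|---|---|
| 0.15 | 43% / 29% | 36% / 48% |
| 0.25 | 81% / 60% | 71% / 88% |
| 0.35 | 97% / 81% | 92% / 99% |

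**4. Are the wide intervals due to the cut-offs?** SE of log OR = ln(upper/lower)/3.92.
- NIHSS ≥5: model 1, ln(115.7/1.9)/3.92 = 1.05 (z = 2.58, P = 0.010); model 3, ln(92.6/1.2)/3.92 = 1.11 (z = 2.13, P = 0.033).
- Aphasia: model 2, ln(129/1.3)/3.92 = 1.17; model 3, ln(87.7/0.7)/3.92 = 1.23.
- Race: model 2, ln(19.8/0.7)/3.92 = 0.85; model 3, ln(62.3/1.1)/3.92 = 1.03. The model 1 race interval is not used, because its printed limits are not symmetric about 10.9 on the log scale (√(1.7×701) = 34.5).

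Within model 3 the three SEs are 1.03, 1.11 and 1.23. Two of these belong to variables with no numeric version.

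**5. How much adjustment a single cut loses.** For a normal covariate with a share q on one side of cut c, the variance left unadjusted is 1 - φ(c)²/[q(1-q)]: 36% at 50:50, 42% at 30:70, 51% at 20:80. For bias in the adherence coefficient:
- Shift 0.5-0.8 SD, correlation 0.5 with outcome: 0.092/0.252 = 37% to 0.178/0.401 = 44% remains.
- Large-sample runs with outcome correlation 0.3 and shifts of 0.47 and 0.70 SD: 0.054/0.137 = 39% and 0.091/0.212 = 43%.
- A further simulation left roughly a third. A linear term leaves about none.

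**6. Effect on type I error in Table IV (n=30/19).** With the cut-off: 4.8% (shift 0.2 SD, correlation 0.2), 5.3% (0.3, 0.3), 5.2% (0.5, 0.3). In these cases the residual bias is 0.01-0.05 SD against an SE of √(1/30+1/19) = 0.29 SD. With shift 0.5-0.8 and correlation 0.5: 6-9%.

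**7. Race and aphasia.** Models 2 and 3 differ only by NIHSS ≥5. The race odds ratio moves from 3.7 to 8.2 and the aphasia odds ratio from 12.9 to 8.0, so both are sensitive to how severity is handled. That does not show how much confounding is left: odds ratios can shift when a covariate is added even without confounding, and the intervals are wide.

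**The case against.** Four stronger readings are tempting, and the document does not support them.

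- **That the cut-offs caused the wide intervals.** Step 4 shows aphasia and race about as imprecise in the same model. The likelier main cause is about 49 patients, 19 of them non-adherent, carrying six or seven covariates. A per-point odds ratio would look narrower partly because its unit is smaller.
- **That an NIHSS effect was missed.** NIHSS ≥5 excludes 1 in both models that contain it. The power comparison measures information discarded. It is also unadjusted: the simulated shares at or above 5 (62% and 39%) imply an odds ratio of about 2.6, against a printed adjusted 14.9, so it does not represent the fitted model.
- **That Table IV is biased through age and BMI.** Neither is reported by adherence or linked to outcome. Baseline NIHSS, the covariate seen to be unbalanced, is already a score there.
- **That coding NIHSS in two ways is a contradiction.** One model studies it as a predictor of adherence; the other adjusts change for baseline. The purposes differ.

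It is also fair to say that the covariates were fixed a priori, that replacing them after results are printed would make a post-hoc specification primary, and that linearity is doubtful for a skewed NIHSS (mean 6.5, SD 4.3). These objections limit the size of the point and the remedy. They leave standing the coding itself, the lack of a stated reason for it, and the fact that numeric terms use no more parameters.

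**Conclusion.** The point holds as a minor one. If relations are graded, the cut at 5 lowers power for NIHSS from about 70% to 35-42%. If there is a true step at 5, the cut-off is the better coding. A cut covariate leaves roughly 30-45% of any linear confounding that runs through it, which concerns severity in the race and aphasia odds ratios and age and BMI in Table IV. The size and direction of that confounding cannot be derived from the document. Over the scenarios tried, type I error ranges from about 5% to 8-9%, with the upper end needing strong assumed confounding. These figures rest on the assumed NIHSS distribution, normal age and BMI, the position of the cuts, and n=49 for Table III. The primary end point, the proportion adherent over 90 days, is unaffected.

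**What to change.** Re-run the Table III and Table IV models with age in years, BMI in kg/m² and, in Table III models 1 and 3, NIHSS as a score, all as linear terms. Check linearity for NIHSS in particular, including whether a few high scores drive the slope. Keep the a priori cut-off models, and show the re-run beside them, labelled as added later. If the two sets differ, temper the conclusions on NIHSS, race, aphasia and the association of adherence with outcome.

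The cost is one re-run on data already recorded, with the same number of parameters. The downsides are a linearity assumption and the post-hoc label.

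### Motor FIM is tested only as raw change, without its own admission score as a covariate, which costs some precision in this sample but does not alter the null result

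*Combined protocol and SAP*

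**What the plan says.** The opening Methods section lists change in motor FIM from admission to 3 to 4 months after discharge among the secondary efficacy end points. The Statistical Analyses section plans comparisons by adherence group of baseline, 3-month and change scores: "motor FIM and cognitive FIM by CPAP adherence using the t-test with unequal variances (Table IV").

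The next sentence of that section plans adjusted models for the association of adherence "with 3-month NIHSS and cognitive FIM change using linear regression". Motor FIM is not in that sentence, yet the motor FIM row of Table IV prints an adjusted P of 0.65 beside the unadjusted 0.83.

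The table footnote defines what both P-values test: "Difference between mean changes in outcome between adherent and non-adherent patients: unadjusted using t-test with unequal variances", and the second "adjusted for age, sex, body mass index, race and baseline NIHSS using linear regression". Admission motor FIM is in neither analysis. A further footnote gives the FIM sample: "n=22 adherent group and n=12 non-adherent". Table IV prints no confidence interval for any outcome and no P-value for the 3-month scores.

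**The concern.** A raw change score is a regression in which the coefficient on the admission score is fixed at 1. If the true coefficient is well below 1, subtracting the admission score adds noise. Table IV shows this directly: the motor FIM change SD exceeds the follow-up SD in both groups (15.7 against 12.1 in adherers, 13.2 against 10.8 in non-adherers).

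The value of a null result lies in the differences it excludes. With 34 patients and a telephone response of about 60% (Efficacy Measures), precision is scarce, and it is worth asking whether the printed analysis gives some away. The issue here is precision. The groups start almost level on motor FIM (48.5 and 47.3), so the choice between change and adjusted follow-up moves the estimate little. Cognitive FIM is different: its 4.4-point baseline gap makes the same choice a question of bias.

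**Working it through.** **Inputs** (Table IV, motor FIM row and its footnote), mean (SD):

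| | n | Admission | 3-month | Change |
|---|---|---|---|---|
| Adherent | 22 | 48.5 (11.2) | 79.7 (12.1) | 31.2 (15.7) |
| Non-adherent | 12 | 47.3 (17.6) | 77.5 (10.8) | 30.2 (13.2) |

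**1. Reproduce the printed unadjusted P.** Welch test on change: difference 31.2 - 30.2 = 1.0; SE = sqrt(15.7²/22 + 13.2²/12) = sqrt(11.20 + 14.52) = 5.07; df 26.3; P = 0.845. Letting the printed values vary within ±0.05 gives P from 0.830 to 0.861, so the printed 0.83 is reached at the edge of rounding. The 95% CI is 1.0 ± 2.054 × 5.07 = -9.4 to 11.4.

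**2. Implied correlation of admission and follow-up.** r = (SD_adm² + SD_fu² - SD_chg²) / (2 × SD_adm × SD_fu).
- Adherent: (125.44 + 146.41 - 246.49) / (2 × 11.2 × 12.1) = 0.09.
- Non-adherent: (309.76 + 116.64 - 174.24) / (2 × 17.6 × 10.8) = 0.66.

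**3. Pooled within-group slope.** The within-group covariances are half the numerators above: 12.68 and 126.08.
- Sxx = 21 × 125.44 + 11 × 309.76 = 6041.6
- Sxy = 21 × 12.68 + 11 × 126.08 = 1653.2
- Syy = 21 × 146.41 + 11 × 116.64 = 4357.65
- Slope = 1653.2 / 6041.6 = 0.27
- Residual SD = sqrt((4357.65 - 0.2736 × 1653.2) / 31) = 11.22
- SE of slope = 11.22 / sqrt(6041.6) = 0.14; 95% CI -0.02 to 0.57. The value 1 lies about five SEs away.

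**4. Follow-up adjusted for admission motor FIM.** Difference = (79.7 - 77.5) - 0.2736 × (48.5 - 47.3) = 2.2 - 0.33 = 1.9. SE = 11.22 × sqrt(1/22 + 1/12 + 1.2²/6041.6) = 4.03. 95% CI on 31 df: -6.4 to 10.1; P = 0.65.

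**5. 3-month score alone.** Difference 2.2; SE = sqrt(12.1²/22 + 10.8²/12) = sqrt(6.66 + 9.72) = 4.05; 95% CI -6.1 to 10.5; P = 0.59.

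**6. Comparison.** 5.07 / 4.03 = 1.26, so the change-score SE is about 26% larger than the adjusted one, and 5.07 / 4.05 = 1.25 times that of the 3-month score alone. Step 1 allows unequal variances and step 4 assumes a common variance. With a common variance for both, the comparison is 5.34 against 4.03 (33% larger). With heteroscedasticity-robust SEs for step 4 (about 3.6 to 3.8), the change SE is 32 to 40% larger. The 26% figure is therefore at the low end of these alternatives.

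**The case against.** Several points on the other side are sound.

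- **The end point is defined as change, so testing change is not an error.** This stands. The fix does not abandon the end point, though: once admission motor FIM is a covariate, the adherence coefficient and its SE are the same whether the outcome is follow-up or change.
- **The more precise comparison is already listed.** The text includes a 3-month comparison, and its SE (4.05) is almost the adjusted one (4.03). This stands, and reduces much of the point to reporting: Table IV gives the 3-month means and SDs but no test or interval.
- **The figures are sample estimates.** Approximate 95% intervals for the correlations are -0.34 to 0.50 (adherent) and 0.14 to 0.90 (non-adherent). Tests of change SD against follow-up SD in paired data give P of about 0.11 and 0.54 by group. So it is not established beyond this sample that change is noisier than follow-up alone. The case for adjustment rests instead on the slope, whose interval excludes 1. The group slopes also differ (0.10 and 0.41), so a common slope is an approximation, and a ceiling may compress follow-up scores (79.7 + 12.1 = 91.8 against a maximum of 91).
- **No conclusion changes.** This stands. The documents name no margin that one interval excludes and the other does not, and they claim no motor FIM equivalence.

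Two stronger readings are tempting. A reader might convert the variance ratio (1.26² ≈ 1.58) into 34 × 1.58 ≈ 54 patients and call that the benefit of the fix. It is not: the ratio compares an unadjusted test with a one-covariate model, whereas the fix adds a covariate to a model that already has five, whose SE is not printed. A reader might also infer from the matching P of 0.65 in step 4 and in Table IV that admission motor FIM was in fact used. The footnote describes a different model, so the match is no evidence of that.

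**Conclusion.** The point holds as a minor precision improvement. The motor FIM P-values in Table IV test raw change, and the adjusted model omits the admission score of the measure being analysed. In this sample the unadjusted change comparison has an SE about 26% larger than an analysis conditioning on admission motor FIM; the interval narrows from -9.4 to 11.4 to -6.4 to 10.1. The loss in the printed adjusted result cannot be computed from the documents.

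It would be wrong to infer that the change score concealed a motor benefit: the estimate moves only from 1.0 to 1.9 points and P stays between 0.59 and 0.65 under the alternatives. Nor does the argument that change is noisier than follow-up carry over to the NIHSS, where the change SD is the smaller in both groups (2.6 against 3.1; 2.2 against 2.6).

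The figures assume that all the motor FIM SDs in Table IV come from the same 22 and 12 patients, as its footnote indicates, and that a common slope is adequate. The groups are not randomised, so change and adjusted follow-up can answer different questions; with a 1.2-point baseline gap this matters little here.

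**What to change.** In the Statistical Analyses section, name a linear regression for motor FIM with admission motor FIM added to the covariates already listed; the outcome may be follow-up or change. In the motor FIM row of Table IV, report the adjusted difference with its 95% CI, and bring the footnote into line with the text. If the cognitive FIM model is also revised to include its admission score, one sentence can cover both components.

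The cost is one degree of freedom, one sentence and one rerun on data already held. The result is expected to remain null; how much the adjusted interval narrows will be known only from the rerun.
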